11.7.13 Headache Pain-Free After Second Dose

Counts and percentages of the number of subjects who are headache pain-free after second dose will be presented at the 0.5, 1, 2, 4, 24, and 48-hour post second dose time points. This summary will be presented by treatment sequence for the ITT-2nd Dose population, and separately for subjects taking a second dose for rescue or recurrence.

Headache pain-free after second dose is defined as experiencing a mild (1), moderate (2) or severe (3) headache at second-dose baseline which becomes none (0) at the summarized time point after a second dose is taken.

Subjects missing a headache severity at baseline or at the summarized time point will not be summarized at that time point.

11.7.14 Time to Headache Pain-Free After Second Dose

The time to headache pain-free after second dose will be presented by treatment sequence using a Kaplan-Meier analysis. This summary will be presented for the ITT-2nd Dose population, and separately for subjects taking a second dose for rescue or recurrence.

The number of subjects experiencing headache pain-free, and the number of subjects censored, will be summarized. The Kaplan-Meier estimates, and 95% confidence intervals calculated using the log-log transformation, of the number of hours for 25%, 50%, and 75% of subjects to experience headache pain-free will be presented. The Kaplan-Meier estimate, and 95% confidence interval, of the probability of experiencing headache pain-free will be presented at the 0.5, 1, 2, 4, and 24-hour post second dose time points.

Time to headache pain-free after second dose is calculated as:

- date/time headache severity is reported as none (0) after second dose –
- date/time of second dosing of a headache that was mild (1) or moderate (2) or severe (3) at

baseline

Subjects who do not report a headache severity of none after dosing, or who report a headache with a severity of none after 24 hours post second dose, will be censored at the time of their last non-missing post second dose headache severity assessment at or before 24 hours. Subjects with missing second dose baseline headache severity will not be considered in time to event analysis for second dose. Subjects who report a headache severity of none (0) at second dose baseline, will be presented in a separate listing as a report at the time of second dose. Subjects who report headache severity of mild (1) or moderate (2) or severe (3) at second dose baseline, will be considered in time to event analysis for second dose.

A figure of the Kaplan-Meier analysis will also be presented.

11.7.15 Headache Relief After Second Dose

Counts and percentages of the number of subjects with headache relief after second dose will be presented at the 0.5, 1, 2, 4, 24, and 48-hour post second dose time points. This summary will be presented by treatment sequence for the ITT-2nd Dose population, and separately for subjects taking a second dose for rescue or recurrence.

Headache relief after second dose is defined as experiencing a moderate (2) or severe (3) headache at second dose baseline which becomes mild (1) or none (0) at the summarized time point after a second dose is taken, or experiencing a mild (1) headache at second dose baseline which becomes none (0) at the summarized time point after a second dose is taken.

Subjects missing a headache severity at baseline or at the summarized time point will not be summarized at that time point.

11.7.16 Time to Headache Relief After Second Dose

The time to headache pain-free after second dose will be presented by treatment sequence using a Kaplan-Meier analysis. This summary will be presented for the ITT-2nd Dose population, and separately for subjects taking a second dose for rescue or recurrence who report headache severity of mild (1) or moderate (2) or severe (3) at second dose baseline,.

The number of subjects experiencing headache relief, and the number of subjects censored, will be summarized. The Kaplan-Meier estimates, and 95% confidence intervals calculated using the log-log transformation, of the number of hours for 25%, 50%, and 75% of subjects to experience headache relief will be presented. The Kaplan-Meier estimate, and 95% confidence interval, of the probability of experiencing headache relief will be presented at the 0.5, 1, 2, 4, and 24-hour post second dose time points.

Time to headache relief after second dose will be calculated as:

date/time headache severity is reported as mild (1) or none (0) after second dose –
date/time of second dosing of a headache that was moderate (2) or severe (3) at second-dose baseline

or as

date/time headache severity is reported as none (0) after second dose –
date/time of second dosing of a headache that was mild (1) at second-dose baseline

Subjects who do not report a headache with severity of mild or none, or who report a headache with a severity of mild or none after 24 hours post second dose, will be censored at the time of their last non-missing post second dose headache severity assessment at or before 24 hours. Subjects with missing second dose baseline headache severity will not be considered in time to event analysis for second dose. Subjects who report a headache severity of none (0) at second dose baseline, will be presented in a separate listing as a report at the time of second dose but not included in this time-to-relief analysis.

A figure of the Kaplan-Meier analysis will also be presented.

11.7.17 MBS-Free After Second Dose

Counts and percentages of the number of subjects who are MBS-free after second dose will be presented at the 0.5, 1, 2, 4, 24, and 48-hour post second dose time points. This summary will be presented by treatment sequence for the ITT-2nd Dose population, and separately for subjects taking a second dose for rescue or recurrence. This summary will be repeated separately for each symptom (nausea, phonophobia, and photophobia) on the ITT-2nd Dose population.

MBS-free after second dose is defined as a lack, post second dose, of the presence of the associated symptom (either nausea, phonophobia, or photophobia) that was identified as the most bothersome symptom at the time of the second dose. The counts and percentages of which symptom was chosen as the most bothersome symptom will also be presented. Subjects who record that none of these symptoms was present at the time of the second dose will be excluded from the MBS analysis.

Subjects who do not provide a symptom rating at the time of second dose will be considered as follows:

- Subjects who record at least one symptom present at the time of second dose, but who do not designate one as most bothersome, will be treated as if all symptoms present are most bothersome and will be considered MBS-free at a given time point post second dose only if all symptoms present at the time of second dose are no longer present at the time point post second dose.

Subjects free of symptoms at second-dose baseline or at the summarized time point will not be summarized at that time point.

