11.7.3 MBS-Free

The endpoint of MBS-free will be summarized at the 0.5, 1, 1.5, 3, 4, 24, and 48-hour post-dose time points. This summary will be presented by treatment group for the ITT, mITT, and PP populations, based on first dose. This summary will be repeated separately for each symptom (nausea, phonophobia, and photophobia) on the ITT population.

Subjects missing symptoms at baseline or at the summarized time point will not be summarized at that time point.

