11.7.18 Time to MBS-Free After Second Dose

The time to MBS-free after second dose will be presented by treatment group using a Kaplan-Meier analysis. This summary will be presented for the ITT-2nd Dose population, and separately for subjects taking a second dose for rescue or recurrence.

The number of subjects experiencing MBS-free, and the number of subjects censored, will be summarized. The Kaplan-Meier estimates, and 95% confidence intervals calculated using the log-log transformation, of the number of hours for 25%, 50%, and 75% of subjects to experience MBS-free will be presented. The Kaplan-Meier estimate, and 95% confidence interval, of the probability of experiencing MBS-free will be presented at the 0.5, 1, 2, 4, and 24-hour post-dose time points.

Time to MBS-free will be calculated as:

date/time a lack of presence of the MBS chosen at the time of second dosing is reported –
date/time of second dosing

Subjects who do not record the disappearance of their second-dose MBS, or who record such a response after 24 hours post second dose will be censored at the time of their last non-missing post second dose symptom assessment at or before 24 hours. Subjects with missing MBS at the time of second dose will be censored at the time of second dose. Subjects who report that no symptoms were present at the time of second dose will be excluded from the analysis.

A figure of the Kaplan-Meier analysis will also be presented.

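### As worded, the second-dose MBS-free summary (SAP 11.7.17) drops subjects with no symptoms left at the time point, so complete responders leave the percentage meant to count them

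*SAP*

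**What the plan says.** SAP 11.7.17 sets the response: "MBS-free after second dose is defined as a lack, post second dose, of the presence of the associated symptom" that the subject named as most bothersome when taking the second dose. Subjects who had symptoms but named none as MBS count as responders "only if all symptoms present at the time of second dose are no longer present at the time point post second dose". The section excludes subjects with nothing to clear: "Subjects who record that none of these symptoms was present at the time of the second dose will be excluded from the MBS analysis". It then closes with: "Subjects free of symptoms at second-dose baseline or at the summarized time point will not be summarized at that time point".

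The neighbouring rules differ. For first-dose MBS-free, SAP 11.7.3 says: "Subjects missing symptoms at baseline or at the summarized time point will not be summarized at that time point". For second-dose pain-free, SAP 11.7.13 says: "Subjects missing a headache severity at baseline or at the summarized time point will not be summarized at that time point", and SAP 11.7.15 uses the same rule for second-dose headache relief. For time to MBS-free after the second dose, SAP 11.7.18 applies its symptom-free exclusion at baseline only: "Subjects who report that no symptoms were present at the time of second dose will be excluded from the analysis".

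Protocol 10.6.1 and 10.6.2 call for summary statistics on MBS freedom by treatment sequence, for rescue and for recurrence, with no exclusion of symptom-free subjects. SAP 5.1, which lists departures from the protocol, does not mention one.

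**The concern.** Having no symptoms at the assessed time is the best outcome this endpoint can record, and such a subject necessarily lacks the MBS. The closing sentence removes that subject at exactly that time point. Its baseline half adds nothing, because the same section already excludes subjects with no symptom at the second dose. Its only new effect is therefore to delete complete responders after dosing.

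The effect of a second dose on MBS, in rescue and in recurrence, is one of the Additional Objectives (Protocol 5.3). This table is its point-in-time result and is repeated for each symptom. If programmed as worded, it would understate MBS freedom in every sequence that has complete responders. It would also disagree with the Kaplan-Meier analysis of the same endpoint.

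**Working it through.** The plan states no figure for this summary, so there is none to reproduce. The check follows the rule through.

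**Inputs.** Take N subjects with at least one symptom at second-dose baseline and complete symptom data at the time point. Let p be the true MBS-free share and f the share of MBS-free subjects with none of the three symptoms left. The documents give neither, so all values below are assumptions. Symptoms here means nausea, phonophobia and photophobia, the three named in 11.7.17.

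**Who is removed.** A non-responder still has a baseline symptom, so is never symptom-free and always stays. Of the Np responders, Npf are symptom-free and are dropped.

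**Reported percentage.** (Np − Npf)/(N − Npf) = p(1−f)/(1−pf). This is below p whenever pf > 0 and p < 1. If symptom-free subjects are kept, the result is p.

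**Illustration, equal f.** True rates are 40% (placebo second dose) and 55% (active second dose), a difference of 15 points. Differences are taken from unrounded rates.

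| f | p = 0.40 | p = 0.55 | Difference |
|---|---|---|---|
| 0.6 | 0.16/0.76 = 21.1% | 0.22/0.67 = 32.8% | 11.8 points |
| 0.8 | 0.08/0.68 = 11.8% | 0.11/0.56 = 19.6% | 7.9 points |
| 0.9 | 0.04/0.64 = 6.25% | 0.055/0.505 = 10.9% | 4.6 points |

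**Odds ratio.** The reported odds are (1−f) × p/(1−p), so f cancels when it is the same in both sequences. The true odds ratio is (0.55/0.45)/(0.40/0.60) = 1.83. As reported with f = 0.8 it is (0.11/0.45)/(0.08/0.60) = 1.83.

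**Unequal f.** Take true rates of 50% and 30%, with f = 0.8 in the better sequence and 0.5 in the other. The table shows 0.10/0.60 = 16.7% against 0.15/0.85 = 17.6%, so a true difference of +20 points appears as −1.0. The odds ratio moves from (0.5/0.5)/(0.3/0.7) = 2.33 to 2.33 × 0.2/0.5 = 0.93.

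**Two groups hit hardest.** A subject with a single symptom at second-dose baseline who loses it is symptom-free, and so dropped, unless a new symptom has appeared. The same holds for a subject who named no MBS, because response there requires all baseline symptoms to be gone.

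**The case against.** The strongest reply is that this is a slip of the pen. The section's own definition and the wording of 11.7.3, 11.7.13, 11.7.15 and 11.7.18 all point to missing data as the intended post-dose exclusion, and an alert programmer would query it. That reading is probably right. But nothing in the SAP overrides the sentence, and it can be programmed exactly as it stands.

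The second reply is that little depends on it. SAP 5.1 calls the second-dose analyses exploratory. SAP 11.7.18 gives Kaplan-Meier probabilities at 0.5, 1, 2, 4 and 24 hours, five of the six time points in 11.7.17, and SAP 11.7.4 tabulates each symptom after the second dose. A literal error would show up against those tables. This stands and limits the weight of the point. The Kaplan-Meier analysis is not a full substitute, because it records when the MBS is reported absent, not the subject's status at each time point.

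Third, SAP 11 makes the odds ratio the default comparison measure, and it is unchanged when f is equal across sequences. That also stands, although dropping responders costs precision and equal f is itself an assumption.

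A reader might also infer more than the text supports:

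- That every responder is lost. Those with another symptom remaining are kept and counted. In the by-symptom repeats, no responder would remain only if the sentence were read as free of that particular symptom.
- That the reported rate falls as the second dose works better. At fixed f it rises with p, from 11.8% to 19.6% above. It falls only as f rises.
- That differences between sequences always shrink. With true rates of 50% and 70% and f = 0.5 in both, the table shows 0.25/0.75 = 33.3% and 0.35/0.65 = 53.8%, a difference of 20.5 points against a true 20.
- That a subject with one baseline symptom can never respond. Such a subject counts if the MBS clears and a different symptom appears.

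**Conclusion.** The point holds as an internal contradiction in SAP 11.7.17. The post-dose half of its closing sentence removes subjects who meet the section's definition of response, and it conflicts with the parallel rules. The percentage is biased downward wherever some, but not all, subjects respond and some responders have no symptom left. How far cannot be known from the documents, since p and f are both assumed: under true rates of 40% and 55%, the reported rates run from 21.1% and 32.8% (f = 0.6) to 6.25% and 10.9% (f = 0.9). Differences in percentages are distorted even when f is equal; the odds ratio is biased only when f differs between sequences, and the direction of effect can then reverse.

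A reader might take this as a threat to the trial's main conclusions. The documents do not support that. The primary and key secondary analyses, the gatekeeping sequence and the second-dose Kaplan-Meier analysis do not use this rule. The effect is confined to one exploratory summary and its by-symptom repeats. It should still be corrected before programming, because following the text gives a wrong table.

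**What to change.** Replace the last sentence of SAP 11.7.17 with: *Subjects with no symptom present at second-dose baseline are excluded; subjects missing a symptom assessment at second-dose baseline or at the summarized time point will not be summarized at that time point; subjects recorded as having no symptoms at the summarized time point are counted as MBS-free.*

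Apply the same rule to the by-symptom repeats. The rule for subjects who named no MBS can stay as it is. The cost is one SAP sentence and about one line of derivation code, with no new data.

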11.7.18 Time to MBS-Free After Second Dose

The time to MBS-free after second dose will be presented by treatment group using a Kaplan-Meier analysis. This summary will be presented for the ITT-2nd Dose population, and separately for subjects taking a second dose for rescue or recurrence.

The number of subjects experiencing MBS-free, and the number of subjects censored, will be summarized. The Kaplan-Meier estimates, and 95% confidence intervals calculated using the log-log transformation, of the number of hours for 25%, 50%, and 75% of subjects to experience MBS-free will be presented. The Kaplan-Meier estimate, and 95% confidence interval, of the probability of experiencing MBS-free will be presented at the 0.5, 1, 2, 4, and 24-hour post-dose time points.

Time to MBS-free will be calculated as:

date/time a lack of presence of the MBS chosen at the time of second dosing is reported –
date/time of second dosing

Subjects who do not record the disappearance of their second-dose MBS, or who record such a response after 24 hours post second dose will be censored at the time of their last non-missing post second dose symptom assessment at or before 24 hours. Subjects with missing MBS at the time of second dose will be censored at the time of second dose. Subjects who report that no symptoms were present at the time of second dose will be excluded from the analysis.

A figure of the Kaplan-Meier analysis will also be presented.

11.7.19 Meaningful headache relief

This summary will be presented based on the e-diary question “Do you have meaningful relief” and subjects responses as “YES” to this question. Number and percentage of subjects with any meaningful headache relief after first dose (mITT population) and second dose (mITT and ITT 2nd dose population) will be summarized for each treatment group in total and for different categories of times after dosing. Median time to meaningful headache relief in hours will also be presented for each treatment group for subjects who took first dose and second dose.

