### 10.3.2 Second Dose Analysis Populations

The analysis populations for the second dose used for rescue or for recurrence will be as defined below. Subjects **must** have taken the second dose and have been considered evaluable for the first dose and primary analysis to be included in the second dose analysis.

**Safety population** All randomized subjects who were considered in the safety population after the first dose and used a second dose of study drug, regardless of whether or not they undergo any study assessments. Subjects are evaluated by the drug they receive, not by the drug to which they are randomized.

**ITT-2nd Dose population** All randomized subjects who were considered ITT after the first dose and used a second dose of study drug and have any post-dose assessments. Subjects are evaluated by the drug to which they are randomized.

**mITT-2nd Dose population** All randomized subjects who were considered mITT after the first dose and used a second dose of study drug and have any post-second dose assessments. Subjects are evaluated by the drug to which they are randomized.

**PP-2nd Dose population** All ITT subjects will be considered per protocol (PP) if they use a second dose for rescue or recurrence of a migraine attack and do not deviate from the protocol.

The 2nd dose ITT, mITT and PP analysis populations will be further qualified by reason for second dose. Subjects will be considered in the 2nd dose rescue populations or 2nd dose recurrence populations as defined:

- **Rescue population:** All randomized subjects who did not achieve headache pain free at 2 hours, completed the 2 hour assessments and took a second dose of study drug between 2 hours and 24 hours.

- **Recurrence population:** All randomized subjects who achieved headache pain free at 2 hours, but then experienced recurrence of mild, moderate or severe migraine pain and took a second dose of study drug up to 24 hours from the first dose.

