4 ANALYSIS POPULATIONS

The following analysis populations will be defined for this study. Subjects' inclusion in or exclusion from these analysis populations will be finalized prior to study unblinding

Randomized population	All randomized subjects. Subjects will be evaluated by the drug to which they are randomized.
Safety population	All randomized subjects who use at least one dose of study drug, regardless of whether or not they undergo any study assessments. Subjects will be evaluated by the drug they use, not by the drug to which they are randomized, when data indicate a difference.
ITT population	All randomized subjects who use at least one dose of study drug and have any post-dose headache severity or symptom assessments. Subjects are evaluated by the drug to which they are randomized.
mITT population	All ITT subjects who treat a migraine attack within four hours of onset. Subjects will be evaluated by the drug to which they are randomized. The mITT population is the primary analysis population.
PP population	All mITT subjects will be considered per protocol (PP) if they do not have major protocol deviations, enumerated below, which might impact the assessment of efficacy. Subjects will be evaluated by the drug to which they are randomized.

Safety-2nd Dose population	All randomized subjects who were considered in the safety population after the first dose and use a second dose of study drug, regardless of whether or not they undergo any study assessments. Subjects will be evaluated by the drug they use, not by the drug to which they are randomized.
ITT-2nd Dose population	All randomized subjects who were considered ITT after the first dose and use a second dose of study drug and have any post-dose headache severity or symptom assessments. Subjects will be evaluated by the drug to which they are randomized.

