5 GENERAL SPECIFICATIONS

This section details the specifications for summarizing all efficacy and safety endpoints.

Continuous variables will be summarized using descriptive statistics, i.e. n (number of subjects with available data), mean, median, standard deviation, minimum, and maximum. For those measures that are analyzed using change from baseline scores, descriptive statistics will also be presented on observed scores, unless otherwise noted.

Minimum and maximum values will be presented to the same precision as the raw data. Mean and median will be presented to one more decimal place than the raw data. Standard deviation will be

presented to two more decimal places than the raw data. P-values will be presented to three decimal places.

Categorical variables will be summarized using counts and percentages. Unless otherwise specified, percentages will be calculated using the numbers of subjects in the summarized population in each treatment group as denominators. Percentages will be presented with a precision of 1 digit after the decimal.

In this study, subject will enter the efficacy data on dosing and post-dose assessments in an e-diary. The e-diary records the date and time of the first dose and of the second dose and is programmed to assess specific time points and assessments as defined in the protocol based on the timing of the dose as recorded. This data is collected in the e-diary when e-diary is in migraine mode. Specifics of Migraine Mode are as below:

- Migraine Mode – First Dose
 - The e-diary enters Migraine Mode **ONLY** if the subject indicates taking his/her first dose of study medication
 - Post Dose Assessments will be completed using the Migraine Questions button at specific time intervals for up to 48 hours after the subject confirms taking study medication

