5.1 Changes and Clarifications from the Planned Analysis

The protocol detailed mITT-2nd Dose and PP-2nd Dose populations. However, the second dose

analyses are all exploratory, and the decision was made to run all exploratory analyses on the ITT and ITT-2nd Dose populations. The mITT-2nd Dose and PP-2nd Dose populations were, therefore, removed.

The protocol stated that statistical testing would be performed to compare demographic data between treatment groups. It was decided that this testing was unnecessary due to the randomization of the study, and these statistical tests were removed from the analysis.

The analyses of the primary efficacy measure and other related measures described in the protocol were limited to headaches that were of moderate or severe intensity at the time of dosing. In keeping with subsequent input to CoLucid from the Food & Drug Administration (FDA), the efficacy endpoints will take into account headaches that were of mild intensity at the time of treatment.

The protocol stated that logistic regression would be used to model efficacy endpoints, but did not detail what method was to be used for non-binary categorical endpoints. The addition of the Cochran-Mantel-Haenszel test is detailed in the relevant sections below to test these endpoints.

Although the protocol did not specify this, it was decided that the exploratory MBS analyses would be repeated separately for each chosen most bothersome symptom (nausea, phonophobia or photophobia). Additionally, a time to MBS-free analysis was added for all MBS endpoints.

The protocol does not mention an additional subgroup analysis but subgroup analysis described in Section 11.8 will be provided.

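### SAP 11.7.19 reports meaningful relief after the second dose on a population that is either the wrong denominator or no longer defined, and groups it by first dose rather than by treatment sequence

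*SAP*

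**What the plan says.** For the number and percentage of subjects with meaningful relief, SAP 11.7.19 uses the mITT population after the first dose. For the later dose it says: "second dose (mITT and ITT 2nd dose population) will be summarized for each treatment group in total".

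Five other places in the SAP bear on this.

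- Section 4 defines one mITT population: "All ITT subjects who treat a migraine attack within four hours of onset". It does not require a second dose.
- Section 4 defines ITT-2nd Dose as "All randomized subjects who were considered ITT after the first dose and use a second dose of study drug", with post-dose assessments also required.
- Section 5 sets the default denominator: "Unless otherwise specified, percentages will be calculated using the numbers of subjects in the summarized population in each treatment group as denominators". Section 11.7.19 states no exception.
- Section 5.1 says that "the decision was made to run all exploratory analyses on the ITT and ITT-2nd Dose populations", and then: "The mITT-2nd Dose and PP-2nd Dose populations were, therefore, removed".
- Section 5.2 presents second-dose analyses by treatment sequence, for both the rescue and the recurrence subpopulation.

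Protocol 10.3.2 did define an mITT-2nd Dose population, as "All randomized subjects who were considered mITT after the first dose and used a second dose of study drug", again with post-dose assessments required.

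**The concern.** A response rate for the second dose should be taken over the people who took it. If mITT in 11.7.19 means the population that section 4 defines, the default denominator counts everyone in the arm who treated within four hours. That includes subjects who were pain-free after one tablet pair and needed nothing more. The percentage then combines two things, how often a second dose was taken and how often it worked, and the first of these depends on how well the first dose worked.

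The grouping adds a second problem. Under SAP 2.3, each lasmiditan first-dose group contains sequences with an active second dose and a sequence with a placebo second dose. A percentage for the whole group mixes the two, so it does not describe the effect of a second active dose, which is one of the additional objectives in Protocol 5.3.

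**Working it through.** **Which population is meant.** The phrase can be read in two ways.

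| Reading | Second dose required? | Defined in the SAP? | Consistent with 5.1? |
|---|---|---|---|
| First-dose mITT | No | Yes, section 4 | No |
| mITT-2nd Dose | Yes (Protocol 10.3.2) | No, removed in 5.1 | No |

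The other second-dose efficacy summaries (11.7.13 to 11.7.18, and the second-dose parts of 11.7.4, 11.7.9 and 11.7.12) use ITT-2nd Dose only. Section 11.7.19 is also missing from the SAP table of contents and from the endpoint list in 3.3. That suggests an addition that was not reconciled with the rest, but does not prove it.

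**Size on the first reading.** The plan gives no figure for this endpoint, so there is none to reproduce.

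- From SAP 2.2: assumed 2-hour pain-free rates of 7.4% (placebo) and 18.8% (200 mg). Not pain-free: 1 − 0.074 = 92.6% and 1 − 0.188 = 81.2%, a difference of 11.4 points.
- Assumed, because the documents do not give them: uptake *u* of a second dose among those not pain-free, 25-100%; relief *r* among takers, 30-70%. Both are set equal in the two arms.

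Ignoring recurrence doses:

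Percentage on mITT = (1 − pain-free rate) × u × r, and gap = 0.114 × u × r.

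| u | r | Placebo | 200 mg | Gap (points) |
|---|---|---|---|---|
| 25% | 30% | 6.9% | 6.1% | 0.9 |
| 50% | 50% | 23.2% | 20.3% | 2.85 |
| 100% | 50% | 46.3% | 40.6% | 5.7 |
| 100% | 70% | 64.8% | 56.8% | 8.0 |

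Gaps are computed before rounding. Among second-dose takers the true difference is zero in every row, and ITT-2nd Dose would show that.

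**Recurrence doses.** Under SAP 4.1 only subjects who were pain-free at 2 hours can take a recurrence dose, and the plan expects more of them on 200 mg. Let *v* be the share of them who re-dose, with the same relief rate. Then P(second dose) = u(1 − p) + v·p, where *p* is the pain-free rate, and the gap becomes 0.114 × r × (u − v). At u = 100% and r = 40%, the gap is 4.6 points with v = 0 and 0.114 × 0.40 × 0.70 = 3.2 points with v = 30%. It would vanish at v = u.

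**Ranking.** Without recurrence doses, 200 mg falls below placebo on mITT unless its relief among takers is at least 0.926 / 0.812 = 1.14 times placebo's.

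- Relief 60% on 200 mg and 50% on placebo, u = 50%: 0.406 × 0.60 = 24.4% against 0.463 × 0.50 = 23.2%. The order is right, but a 10-point advantage has shrunk to 1.2 points.
- The same relief rates, with assumed second-dose use of 40% on 200 mg and 60% on placebo: 0.40 × 0.60 = 24% against 0.60 × 0.50 = 30%. The order is reversed.

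**The case against.** The strongest reply is that the closing words of the phrase, 2nd dose population, govern both terms, so mITT-2nd Dose is meant. The sentence does contrast a first-dose population with a second-dose one, and Protocol 10.6 made mITT-2nd Dose the primary population for second-dose analyses. On that reading no non-taker enters the denominator and there is no bias. This stands as a fair reading, but it leaves the programmer with a population that the SAP has deleted.

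A correctly restricted ITT-2nd Dose summary is planned on either reading, and the median time is limited to subjects who took the dose. Section 5.2 also restricts second-dose analyses to data from the second dose onward, which a non-taker cannot have. But 5.2 sets no denominator, and section 5 does.

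The conflict with 5.1 carries limited weight by itself, since 11.7.1 and 11.7.3 also add mITT and PP for first-dose exploratory endpoints. There the denominator is still people who took the dose in question. Likewise, 11.7.18 also presents its second-dose results by treatment group, so 11.7.19 is not alone in departing from 5.2.

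A reader might infer that the arm needing fewer second doses will necessarily look worse. The documents do not support that. It requires the first reading, relief among takers that does not offset the lower use, and recurrence dosing that does not close the gap.

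**Conclusion.** The population statement in 11.7.19 is defective on either reading: it gives the wrong denominator, or it names a set that no longer exists in the SAP. The grouping conflicts with 5.2 and pools active with placebo second doses within each lasmiditan arm.

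The distortion exists only on the first reading. There the percentage for the arm with fewer second doses is pulled down, by about 1 to 8 points for 200 mg against placebo. This rests on the plan's pain-free rates, equal assumed uptake and relief in the two arms, and no recurrence doses. These sizes are illustrations, not predictions.

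Section 11.7.19 is descriptive and exploratory and specifies no treatment comparison. The primary and key secondary tests and their gatekeeping order are untouched. Severity is low.

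**What to change.** In SAP 11.7.19, for the second dose only:

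- delete the words *mITT and*, so that the summary uses the ITT-2nd Dose population alone;
- state that the denominator is subjects who took a second dose;
- replace treatment group with treatment sequence;
- present rescue and recurrence separately, as 5.2 requires.

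This settles both readings. It changes a few words of the SAP and the specification of one exploratory summary. It needs no new data and touches no confirmatory analysis.
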